TITLE: Combined effect of tDCS and motor or cognitive activity in patients with Alzheimer's Disease: a proof-of-concept pilot study

NCT Number: NCT06619795

02/10/2024

The aim of this study will be to evaluate the effectiveness of combining tDCS with motor or cognitive activities on cognitive functions in patients with AD. A secondary aim will be to investigate whether tDCS will have a different impact when combined with motor versus cognitive activities.

Materials and Methods

The study will be a double-blind randomized controlled trial (RCT) that will compare the effects of anodal and sham tDCS combined with motor or cognitive activity on cognitive performance in AD patients. The research team will consist of "evaluators" and "treatment providers." The neuropsychologist evaluator will be responsible for measuring outcomes and will remain unaware of the group assignments. Additionally, to assess the presence of a placebo effect or the absence of an effect from the anodal stimulation, and to reduce potential bias, participants will also be kept unaware of the type of stimulation being administered. In contrast, the treatment providers, including neuropsychologists and physiotherapists, will be informed about the treatment but will not know the type of tDCS stimulation used (anodal or sham) (Cotelli et al., 2014).

Participants

Patients with AD will be recruited from the Mons. A. Mazzali Foundation (Mantua). The inclusion criteria will be: Mini Mental State Examination (MMSE) >15, good level of compliance, treatment with acetylcholinesterase inhibitors (e.g., donepezil, rivastigmine), and no modifications to medication in the last four months. The exclusion criteria will be: behavioral disorders (e.g., aggressiveness), alcohol abuse, orthopedic conditions with a risk of falls, respiratory disorders, uncorrected severe auditory or visual deficits, history of epileptic fits, use of anti-epileptic medication, metallic body implants, pacemaker, and psychiatric, neurological, systemic, or metabolic disorders.

Following a simple software-generated randomization scheme (www.randomization.org), patients will be allocated to one of four groups after the baseline evaluation. Unbalanced randomization will be applied. The randomization list will not be disclosed to the assessors or treatment providers but will be known only to the principal investigator (CF).

Treatment procedures

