The tDCS stimulation will be performed using a BrainSTIM stimulator (EMS). A pair of saline-soaked electrodes will be placed and secured on the patients. The anode (25 cm^2 , 5x5 cm) will be positioned over the left dorsolateral prefrontal cortex (DLPFC) following the 10–20 system (F3-F7 position), and the cathode (35 cm^2 , 7x5 cm) will be placed above the shoulder on the opposite side. The stimulation procedure will be adapted to align with the prevalent literature, as the DLPFC montage is widely used (Pillonni et al., 2022; Fonte et al., 2021). The intensity of the stimulation will be set at 2mA and applied for the first 15 minutes of either cognitive or motor activity (45 minutes total).

The electrode placement and parts of the stimulation procedure will follow the protocol described by Cotelli and colleagues in 2014 (Cotelli et al., 2014). To ensure safety, the current density of the active electrode will be kept within the limits established by Poreisz and collaborators in 2007 and Nitsche and collaborators in 2008. In the sham condition, the current will be turned off 10 seconds after the stimulation starts and turned back on during the final 10 seconds, so that participants will be unable to discern whether the stimulation is real or sham (Poreisz et al., 2007; Nitsche et al., 2008).

Evaluation procedures

Primary and secondary outcomes will be measured by the same blinded examiner. Patients will be evaluated before treatment (T0), immediately after treatment (T1), and at a one-week follow-up (T2). Cognitive assessments will be conducted in a single session lasting one hour. The tests used in the assessment are described below.

- Primary Outcome

The primary outcome will be the Mini Mental State Examination (MMSE), used to assess global cognitive impairment (Folstein et al., 1975).

- Secondary Outcomes

The secondary outcomes will include:

- Picture Recognition (PR) is a subtest of the Rivermead Behavioral Memory Test-3, an ecological memory battery resembling everyday tasks, with the aim to measure daily memory function (Beschin et al., 2013).
- Digit Span Test- Forward (DSF), used to measure span of immediate verbal recall. The examiner presents digits verbally at a rate of one per second (Monaco et al., 2013).
- Digit Span Test- Backward (DSB), used to measure working memory (Monaco et al., 2013).
- Phonemic Fluency Test (PFT), used to measure processing speed, language production and executive functions (Zappalà et al., 1995).

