- Visual Search Test (VST), to assess visual-selective attention (Spinnler & Tognoni, 1987).
- Sustained Attention to Response Test (SART): used to evaluate sustained attention and control inhibition. In the test, participants view a computer monitor on which a random series of single digits are presented at the regular rate of 1 per 1.15 seconds (Robertson et al., 1997).
- Neuropsychiatric Inventory (NPI) to evaluate the presence, frequency and severity of behavioral disorders (Cummings et al., 1994).

Statistical analysis

Data from all randomized patients will be assessed. The Kruskal-Wallis test will be used to measure baseline homogeneity for all outcome measures across the four groups. The Mann-Whitney U test will be employed to examine the effects of tDCS by comparing MotA+CogA versus MotS+CogS between T1 and T0 (T1-T0) and between T2 and T0 (T2-T0). Further analysis will investigate differences in performance between the MotA and CogA groups from T1 to T0 (T1-T0) and from T2 to T0 (T2-T0). The alpha level for significance will be set at $P < 0.05$.

Statistical analysis will be conducted using the Statistical Package for Social Science (SPSS) for Macintosh, version 26.0 (IBM SPSS Inc, Armonk, NY, USA).

To determine the sample size, based on the study by Khedr and colleagues, an effect size of 1.15 will be calculated using G*Power 3.1.9.4 software. With an effect size of 1.15, an alpha of 0.01, and a power of 0.90, a total of 48 patients will be required to detect a significant treatment effect (Khedr et al., 2019).

REFERENCES

3. Khedr, E. M.; Salama, R. H.; Abdel Hameed, M.; Abo Elfetoh, N.; Seif, P. Therapeutic Role of Transcranial Direct Current Stimulation in Alzheimer Disease Patients: Double-Blind, Placebo-Controlled Clinical Trial. *Neurorehabilitation and neural repair* 2019, 33(5), 384–394. doi:10.1177/1545968319840285.
4. OSF Registries. Available online: <https://osf.io> (accessed on 30 August 2024).

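### The main tDCS test pools motor and cognitive patients and leaves out activity, a randomised factor, so it can lose power and cannot correct a chance imbalance in activity mix

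*Combined protocol and SAP*

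**What the plan says.** Under Participants, "patients will be allocated to one of four groups after the baseline evaluation". Treatment procedures defines these as anodal or sham stimulation crossed with motor or cognitive activity (MotA, CogA, MotS, CogS). The same Participants paragraph describes the allocation as simple ("Following a simple software-generated randomization scheme") and adds "Unbalanced randomization will be applied", without giving a ratio. The primary outcome is the MMSE.

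For the main aim, the Statistical analysis section uses a Mann-Whitney U test for the effect of tDCS, "comparing MotA+CogA versus MotS+CogS between T1 and T0 (T1-T0) and between T2 and T0 (T2-T0". No stratification, covariate or factorial model is stated. Two other analyses are described. A Kruskal-Wallis test checks whether the outcome measures are homogeneous at baseline. Then: "Further analysis will investigate differences in performance between the MotA and CogA groups". Neither adjusts the tDCS test for activity.

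The opening statement of aims gives activity a role: "A secondary aim will be to investigate whether tDCS will have a different impact when combined with motor versus cognitive activities".

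**The concern.** Activity is assigned by the same randomisation as stimulation, and the plan treats it as something that may matter. It compares MotA with CogA and has a secondary aim about it. The cognitive sessions train memory and start with orientation; the motor sessions are endurance and resistance exercise. The primary outcome is a global cognitive score. A difference in MMSE change between the two activities is therefore plausible, though the documents give no size for it.

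If there is one, the pooled test suffers in two ways:

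1. Even with an equal mix in both arms, the activity difference remains in the within-arm spread and reduces power.
2. If the motor:cognitive mix differs between the pooled arms, part of the activity effect appears as a tDCS effect, in either direction. With 48 patients and simple randomisation such a difference is not rare, and the trial draws only one list.

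**Working it through.** **Inputs from the documents.** N = 48, d = 1.15, power 0.90 and alpha 0.01 for sample size; alpha 0.05 for analysis (all from Statistical analysis); four groups and simple allocation (Participants).

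**Assumptions.** Two-sided tests; normal errors with SD 1 within each group; an additive activity effect g of 0, 0.3, 0.5 or 1 SD; and, because no ratio is given, either 12 per group or simple allocation with equal targets. A smaller tDCS effect (d = 0.6 or 0.8) is shown beside the planned 1.15.

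**The plan's own figure.** The normal approximation gives n per arm = 2(2.576 + 1.282)² / 1.15² = 22.5, so 23 per arm and 46 in total. The exact t-test calculation gives 25 per arm, 50 in total, with 89.7% power at 24 per arm. The stated 48 is thus reproduced to within 2 patients, as a plain two-group comparison in which activity does not appear.

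**Dilution by formula (24 per arm, equal mix).** Pooled SD = √(1 + g²/4), and effective d = 1.15 / pooled SD.
- g = 0.5: SD 1.031, d = 1.116. t-test power falls from 89.7% to 87.5% at alpha 0.01, and from 97.4% to 96.6% at 0.05.
- g = 1: SD 1.118, d = 1.029. Power falls to 80.5% at alpha 0.01, and to 93.7% at 0.05.

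**Simulated power, 12 per group, pooled Mann-Whitney / van Elteren (40,000 trials per setting).**

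| d, alpha | g = 0 | g = 0.3 | g = 0.5 | g = 1 |
|---|---|---|---|---|
| 0.6, 0.05 | 0.505 / 0.494 | 0.495 / 0.492 | 0.481 / 0.493 | 0.404 / 0.491 |
| 0.8, 0.05 | 0.752 / 0.738 | not run | 0.727 / 0.737 | 0.664 / 0.740 |
| 1.15, 0.05 | 0.965 / 0.961 | 0.965 / 0.963 | 0.960 / 0.962 | 0.940 / 0.961 |
| 1.15, 0.01 | 0.874 / 0.860 | 0.870 / 0.863 | 0.858 / 0.858 | 0.788 / 0.858 |

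The normal-theory pair at d = 0.6, alpha 0.05 and g = 0/0.3/0.5/1 is: pooled t test 0.532/0.524/0.507/0.435; linear model with activity 0.532/0.532/0.532/0.530.

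With simple random lists in place of fixed groups, d = 1.15 and g = 0/0.5/1 give, pooled / van Elteren: 0.964/0.956, 0.954/0.956 and 0.915/0.953 at alpha 0.05; 0.864/0.845, 0.838/0.841 and 0.754/0.841 at alpha 0.01.

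**How often the mix differs.** Over simple lists of 48 with equal targets, the share of cognitive patients differs between the pooled arms by at least 10 points in 49%, 20 points in 18%, 25 points in 9% and 33 points in 2.4%. With 2:2:1:1 targets, the 20- and 33-point figures are 20% and 3.3%.

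**Shift in the estimate.** Shift = g × difference in cognitive share. For a 20-point difference: 0.3 × 0.20 = 0.06, 0.5 × 0.20 = 0.10 and 1 × 0.20 = 0.20 SD.

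**Type I error of the pooled test at nominal 5%, no tDCS effect, equal-target lists.**

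| Lists | g = 0.3 | g = 0.5 | g = 1 |
|---|---|---|---|
| All | 4.9% | 5.1% | 4.8% |
| Mix differs by 20 to 33 points (16% of lists) | 5.4% | 6.3% | 8.8% |
| Mix differs by 33 points or more (2.4%) | 6.4% | 9.4% | 19% |

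Van Elteren stays at 4.7% to 5.4% throughout. At g = 1 the pooled test is conservative when the mix is close: 3.0% below a 10-point difference and 4.7% at 10 to 20 points.

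**Both directions.** As an illustration only, take d = 0.8, alpha 0.05, g = 0.5, with cognitive activity the better one. Groups of 16/8/8/16 (MotA/CogA/MotS/CogS) give the pooled test power 0.521, and 8/16/16/8 gives 0.878. The stratified test gives 0.686 in both.

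**The case against.** Comparing all anodal with all sham patients is a legitimate marginal analysis of a crossed design and answers the main aim. Averaged over lists its type I error is right, and with the same expected mix in both arms the contrast is unbiased. At the planned effect and alpha 0.05, the gain from stratifying is nil at 0.3 SD, 0.2 points at 0.5 SD and about 2 points at 1 SD in equal groups. The larger gains need a 1 SD activity effect, nearly as large as the planned tDCS effect, and nothing in the documents supports that size. At d = 0.6 even the stratified test has under 50% power. A 0.10 SD shift is small beside a standard error of √(2/24) = 0.29 SD. If the list fixes the group sizes, the imbalance frequencies do not apply. Van Elteren also has a price when activity has no effect: 1 to 2 points on average, and more in a badly unbalanced list (0.750 against 0.687 at d = 0.8, alpha 0.05, groups 16/8/8/16). Finally, the secondary aim concerns an interaction, which neither remedy tests.

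All of this stands, and it limits the size of the point. It does not remove it. Being right on average does not correct the one list drawn, and the tDCS effect may be smaller than 1.15 SD. In equal groups the linear model costs essentially nothing when activity is irrelevant (0.532 against 0.532). The simulations used continuous data, but rounding to integers with ties, as for MMSE change, does not change the picture. The interaction question is separate and remains open.

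**Conclusion.** The concern holds as a worthwhile improvement, not as an error that invalidates the test. The planned comparison omits a randomised factor that the plan itself regards as of interest.

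If activity affects MMSE change, the power lost is negligible at 0.3 SD, about 1 point or less at 0.5 SD, and 2 to 9 points at 1 SD in the settings tabulated. About one simple list in five or six has a mix difference of 20 points or more. In those lists the estimate is off by at least 0.06, 0.10 or 0.20 SD for activity effects of 0.3, 0.5 or 1 SD, with no correction planned.

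The figures rest on assumed activity effects, additive effects, normal errors, and either equal groups or unrestricted equal-target allocation. The imbalance would be systematic, and not just chance, only if the unstated unbalanced ratio gave different motor:cognitive splits in the anodal and sham arms. The documents do not say whether it does.

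**What to change.** In Statistical analysis, prespecify that the tDCS comparison of MMSE change is stratified by activity. Either of two forms will do:

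- a van Elteren (stratified Wilcoxon) test, which keeps the rank-based approach; or
- a linear model of MMSE change with tDCS and activity as factors.

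Report the tDCS effect with a 95% confidence interval, from the model or as a stratified Hodges-Lehmann estimate. Where the allocation is described, one clause should say whether the motor:cognitive split is meant to be the same in both stimulation arms.

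The cost is one or two sentences and no new data. The linear model uses one degree of freedom and runs in the SPSS version already named. Van Elteren gives up about 1 to 2 points of power on average if activity has no effect. Fixing the choice now also avoids deciding on adjustment after the realised mix is known.

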The real tDCS groups will receive anodal stimulation combined with either motor activity (MotA) or cognitive activity (CogA). The sham tDCS groups will receive sham stimulation combined with motor activity (MotS) or cognitive activity (CogS).

Each group will undergo 45 minutes of activity, with the first 15 minutes performed simultaneously with tDCS stimulation. Treatments (45 minutes) will be administered for two weeks, five times per week (Cotelli et al., 2014)..

During the study, participants will not engage in any other motor or cognitive activities.

Motor activity

A standardized sequence of motor exercises will be established. A physiotherapist will conduct the individual motor activity, which will include moderate-intensity endurance and resistance training. Each session will begin with a 5-minute warm-up and conclude with a 5-minute cool-down, including active joint mobilization. Subsequently, patients will engage in endurance exercises, which will be

randomly ordered and divided among cycling on a cycle ergometer, walking on a platform, and arm cranking on a specialized ergometer (Fonte et al., 2019).

Cognitive activity

A neuropsychologist will conduct individual cognitive activities, focusing on stimulating residual cognitive abilities, particularly memory. The cognitive stimulation will be tailored to the severity of each patient's cognitive decline. Each session will begin with an orientation exercise, followed by oral and paper-and-pencil tasks targeting specific cognitive functions. These exercises will aim to encourage natural reminiscence processes while also focusing on the present, enhancing social interaction and mood. Multisensory stimulation will also be incorporated.

The structure of the neuropsychological treatment will be modeled after a study conducted by Spector et al. in 2003, which involved 201 dementia patients (Spector et al., 2003). This approach demonstrated positive outcomes in several cognitive domains, as well as improvements in quality of life, while maintaining a high level of feasibility and adaptability (Fonte et al., 2019; Spector et al., 2003).

tDCS procedure

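### The secondary aim is a tDCS-by-activity interaction, but the planned MotA versus CogA comparison leaves out both sham groups and cannot isolate it

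*Combined protocol and SAP*

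**What the plan says.** The opening paragraph on aims states: "A secondary aim will be to investigate whether tDCS will have a different impact when combined with motor versus cognitive activities".

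Treatment procedures describes a design with two factors, stimulation and activity. On active stimulation it says: "The real tDCS groups will receive anodal stimulation combined with either motor activity (MotA) or cognitive activity (CogA". Two further groups, MotS and CogS, pair the same two activities with sham.

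Statistical analysis plans two between-group comparisons of change scores. The main one is a Mann-Whitney test "comparing MotA+CogA versus MotS+CogS between T1 and T0 (T1-T0) and between T2 and T0 (T2-T0", which pools over activity. The other is "Further analysis will investigate differences in performance between the MotA and CogA groups from T1 to T0 (T1-T0", and the same for T2-T0. No test is named for this second comparison; Mann-Whitney is inferred from the sentence before it.

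The only analysis using four separate groups is the Kruskal-Wallis test, and it is for baseline homogeneity. No interaction is planned, and neither is MotA vs MotS, CogA vs CogS or MotS vs CogS.

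**The concern.** The impact of tDCS is its effect relative to sham. Whether that impact differs by activity is the contrast (MotA-MotS)-(CogA-CogS), which needs all four groups. In MotA vs CogA the stimulation does not vary, so the comparison contains no estimate of a tDCS effect in either activity.

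It would answer the aim only if motor and cognitive activity alone produced the same change. The plan neither states nor tests this, and its own text gives reason for doubt. The cognitive programme aims mainly at memory, and the Cognitive activity section says: "Each session will begin with an orientation exercise, followed by oral and paper-and-pencil tasks targeting specific cognitive functions". The motor programme is endurance and resistance exercise. Every outcome except the NPI is a cognitive test.

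The error can run in both directions. A difference between the activities could be read as a different tDCS effect, or a real difference in tDCS effect could be hidden by an activity difference of opposite sign.

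**Working it through.** **Inputs from the documents.** Four groups; total N = 48; effect size 1.15; significance level 0.05 for the analysis and 0.01 for the sample size. The allocation is called unbalanced, but no ratio is given.

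**Assumptions.** 12 patients per group, with unequal cells shown as a range; two-sided tests; normal change scores with a common SD, used as the unit throughout.

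**1. The plan's own figure.** The plan says: "With an effect size of 1.15, an alpha of 0.01, and a power of 0.90, a total of 48 patients will be required". For two equal groups, the normal approximation is n per group = 2(2.576 + 1.282)² / 1.15² = 22.5, rounded up to 23, or 46 in total. The two-sided t-test needs 50 and has power 0.897 at 24 vs 24. So 48 fits a two-group anodal-versus-sham comparison; it was not derived for the secondary aim.

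**2. What the planned comparison estimates.** Writing each group name for its mean change:

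MotA - CogA = (MotS - CogS) + [(MotA - MotS) - (CogA - CogS)]

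The first term is the activity difference under sham. The second is the quantity in the aim. This is an identity and needs no assumption.

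**3. Consequences.** Simulation with 10,000 runs, 12 per group and level 0.05, comparing the Mann-Whitney test of MotA vs CogA with a t-test of the four-group interaction contrast:

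| Activity difference (size) | Difference in tDCS effect | MotA vs CogA significant | Interaction significant |
|---|---|---|---|
| 0 | 0 | 4% | 5% |
| 0.5 SD | 0 | 19% | 5% |
| 1.0 SD | 0 | 60% | 5% |
| 1.15 SD | 0 | 73% | 5% |
| 1.0 SD, opposite direction | 1.0 SD | 4% | 40% |
| 0 | 1.15 SD | 73% | 49% |

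A separate run of 5,000 gave 38% for MotA vs CogA at an activity difference of 0.75 SD with equal tDCS effects.

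The figures depend on cell size. At a 1.0 SD activity difference, the false-signal rate is about 45% with 8 vs 8, 56% with 8 vs 16 and 75% with 16 vs 16.

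**4. Precision of the correct contrast.**

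- SE(MotA-CogA) = √(2/12) = 0.41 SD.
- SE(interaction) = √(4/12) = 0.58 SD, which is √2 times as large.
- With 44 degrees of freedom, the 95% confidence interval extends 2.015 × 0.577 = 1.16 SD either side of the estimate.
- Power at 0.05 (noncentral t) is 16% for an interaction of 0.575 SD, 40% for 1.0 SD and 49.5% for 1.15 SD.
- With cells of 14/14/10/10 or 16/16/8/8, power at 1.15 SD is 48.5% or 45%.
- The detectable difference with equal cells is 1.65 SD at 80% power and 1.91 SD at 90%.
- For 90% power, total N would be about 132 for 1.15 SD and about 512 for 0.575 SD.

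**The case against.** The best defence is that this is a proof-of-concept pilot, and the comparison is introduced only as further analysis of performance in the two groups. Read literally, that describes a fair comparison of two combined treatments. The main anodal-versus-sham comparison is unaffected. This softens the point but does not remove it: if MotA vs CogA is only a comparison of combined treatments, the single stated secondary aim has no analysis at all.

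A second argument is precision. If the activities alone were equivalent, MotA vs CogA would be the stronger test (73% against 49% in the last row of the table). That is true, but the gain rests wholly on an equivalence that the plan does not justify. Otherwise the smaller standard error belongs to a different quantity.

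Third, the sizes are illustrative. The activity differences come from no document, equal groups sit badly with the stated unbalanced randomization, and the 4% masking case is built so that the two effects cancel exactly. These limits stand, which is why ranges are given. They do not touch the identity in step 2.

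Finally, the four-group analysis gives an imprecise estimate, not a firm answer. Interaction plus two within-activity contrasts, over eight outcomes and two time points, makes 3 × 8 × 2 = 48 estimates. This also stands and is dealt with in the fix.

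**Conclusion.** The concern holds. As written, the planned comparison mixes the activity difference with the difference in tDCS effect, and no other planned analysis separates them. The T2-T0 comparison has the same fault. This follows from the definition of the groups and depends on no numerical assumption.

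The practical size does depend on assumptions: cell sizes, two-sided Mann-Whitney testing, normal change scores with equal SD, and the size of the activity difference. Under them, false signals go from about one trial in five at a 0.5 SD activity difference to about three in five at 1.0 SD. The mismatch should be corrected before results are seen, because it affects one of only two stated aims and can mislead in either direction.

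**What to change.** Replace MotA vs CogA as the analysis of the secondary aim with the tDCS-by-activity interaction in all four groups:

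- Fit a linear model for the change score, or for the T1 or T2 score adjusted for T0, with terms for tDCS, activity and their product.
- Report (MotA-MotS)-(CogA-CogS) with a 95% confidence interval, and the tDCS effect within each activity (MotA vs MotS, CogA vs CogS) with intervals.
- Because the plan is otherwise rank-based, add a permutation or aligned-rank version of the interaction test as a check.
- Label the analysis exploratory and state its expected precision. Name one interaction as the main one, for example on the MMSE at T1-T0, and treat the other outcomes and T2 as descriptive.
- If MotA vs CogA is kept, name its test and describe it as a comparison of two combined treatments, not of tDCS impact.

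The cost is wording in the statistical section. All four groups are already randomised and assessed, so no new patients or data are needed. The price is a wider interval: with 48 patients, the result can inform a later trial but is unlikely to settle the question.

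### One P < 0.05 rule covers all secondary tests, 14 of them real versus sham tDCS, and claims of effect are not confined to one MMSE contrast

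*Combined protocol and SAP*

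**What the plan says.** In the combined protocol and SAP, the Evaluation procedures section names MMSE as the single primary outcome. It then lists seven others, introduced by "The secondary outcomes will include": PR, DSF, DSB, PFT, VST, SART and NPI. Assessments are at T0, T1 and T2.

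The Statistical analysis section plans two comparisons, each on the T1-T0 and the T2-T0 change:

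- Real against sham: "The Mann-Whitney U test will be employed to examine the effects of tDCS", with MotA and CogA pooled against MotS and CogS.
- Motor against cognitive activity under real stimulation: "Further analysis will investigate differences in performance between the MotA and CogA groups". No test is named for this one.

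The significance rule is a single sentence: "The alpha level for significance will be set at" P < 0.05. No adjustment, gatekeeping order or exploratory label is attached to any of these tests. An alpha of 0.01 appears only in the sample-size sentence.

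**The concern.** A rule that calls each result significant at 0.05, applied across many outcomes, times and comparisons, will produce some significant results when nothing is going on. Most of the secondary measures are tied to a particular function, such as daily memory, working memory, executive function or attention. A single chance result could therefore be read as an effect of tDCS on that function, and nothing in the plan says that it should not be. The stated aim concerns cognitive functions in general, so a secondary finding would fit it naturally.

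The primary outcome has a smaller version of the same problem. MMSE is compared between real and sham twice, at T1-T0 and T2-T0, and the plan does not say which of the two decides the question.

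**Working it through.** **The plan's own figure.** The plan states no overall error rate. Its one computed figure is the total of 48, from an effect size of 1.15, alpha 0.01 and power 0.90. Assume a two-sided test and equal groups (the plan says allocation is unbalanced but gives no ratio). Then n per group = 2(z₀.₉₉₅ + z₀.₉₀)²/d² = 2(2.576 + 1.282)²/1.15² = 22.5, rounded up to 23, for a total of 46. The t-test version gives 50, and t-test power at 24 per group is 0.897. So 48 is reproduced to within two patients, and the stricter 0.01 was used for sizing but not for the decision rule.

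**Step 1: count the tests.** Inputs: seven secondary outcomes (Evaluation procedures); two change scores and two comparisons (Statistical analysis). Assumptions: one score per instrument, and every secondary outcome in both comparisons.

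- Real versus sham: 7 × 2 = 14.
- MotA versus CogA: 7 × 2 = 14.
- Total: 28, or 32 with the four MMSE tests.

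**Step 2: expected false positives if all nulls are true.** This does not depend on correlation.

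- 14 × 0.05 = 0.7 among the tDCS tests.
- 28 × 0.05 = 1.4 among all secondary tests.

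**Step 3: chance of at least one, if independent.**

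- 1 − 0.95¹⁴ = 51.2%.
- 1 − 0.95²⁸ = 76.2%.

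**Step 4: allow for correlation.** The documents give no correlations, so these are assumed. The figures for 28 tests come from 400,000 multivariate normal draws with two-sided 0.05 tests, taking the two comparisons as independent. That is reasonable: under the null with equal variances, the MotA−CogA difference in means is uncorrelated with the pooled MotA+CogA mean, whatever the group sizes. The figure for 14 tests then follows as 1 − √(1 − figure for 28). With T1/T2 correlation 0.7:

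| Between-outcome correlation | 14 tDCS tests | All 28 |
|---|---|---|
| 0 | 45.7% | 70.5% |
| 0.3 | 41.4% | 65.7% |
| 0.5 | 35.6% | 58.5% |
| 0.6 | 31.8% | 53.5% |
| 0.7 | 28.0% | 48.1% |

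Simulated Mann-Whitney tests with an assumed 12 patients in each of the four groups agree closely for all 28: 67% at a between-outcome correlation of 0.3 and 61% at 0.5, again with T1/T2 correlation 0.7.

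**Step 5: the two MMSE tDCS tests.** If independent, 1 − 0.95² = 9.75%. From the bivariate normal, the chance of at least one false positive is 9.1% at a T1/T2 correlation of 0.5, 8.3% at 0.7 and 7.8% at 0.8.

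**The case against.** The case for leaving the plan alone has several parts.

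- **The plan does rank things.** One outcome is primary and the rest are secondary. The comparison between activities is a secondary aim and a further analysis. The title calls the study a proof-of-concept pilot. This is correct, and a reader who infers that there is no ordering at all goes too far. What is missing is any statement that the ordering governs which results can be claimed. The aim is still worded as evaluating effectiveness, and the sample is sized to detect a significant effect.
- **Half of the 28 tests cannot yield a false tDCS claim.** MotA and CogA both receive real stimulation. This stands in full: for a claim about tDCS the family is 14 tests, with 0.7 false positives expected.
- **More likely than not is conditional.** A reader might take the 76% to mean that a false tDCS finding is more likely than not. The documents do not support that. The 76% needs all nulls true, independence and all 28 tests. With T1/T2 correlation of 0.7 or 0.8, the figure for 28 passes below one half between outcome correlations of 0.6 and 0.7. For the 14 tDCS tests it is 51% only under independence, and below one half in every correlated case in the table.
- **The count is partly inferred.** The text does not say outright that each secondary outcome enters both comparisons, though it excludes none. Several SART or NPI scores would raise the count.
- **Formal adjustment is costly in a pilot.** This also stands. The first Holm step over 14 tests is 0.05/14 = 0.0036. Assuming 24 per arm and a t test, power for d = 0.8 falls from 77% to 39%. A reader might infer that adjustment is obligatory; it is not, since an exploratory label answers the point.

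Nor do the documents contain a reporting rule, so it cannot be said that a chance result would be published as a domain effect. It can only be said that the plan permits it.

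**Conclusion.** The point holds in a bounded form. One rule of P < 0.05 applies to every test, without adjustment or exploratory label, and does not restrict claims of effect to the primary outcome. The chance of at least one false secondary tDCS result is about 28% to 41% under the assumed correlations and 51% under independence, against a nominal 5%. For all 28 secondary tests it is about 48% to 66%, or 76% if independent. These figures rest on all null hypotheses being true, one score per instrument, all seven outcomes in both comparisons, and correlations that the documents do not supply.

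The primary question is only mildly affected, at about 8% to 9% for two MMSE tests, but the plan should still say which of them decides it.

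**What to change.** Before unblinding, add two statements to the Statistical analysis section:

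1. Only the MMSE real-versus-sham contrast at one named time (for example T1-T0) can support a claim of effect at P < 0.05. The other MMSE time is supportive.
2. All seven secondary outcomes, and all MotA-versus-CogA comparisons including MMSE, are reported as estimates with 95% confidence intervals, labelled exploratory, with no statement of significance.

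Holm adjustment across the 14 secondary tDCS tests may be added if the sponsor wants formal secondary inference, at the loss of power shown above. It is not needed if the second statement is adopted.

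The change needs no extra patients, visits or measurements. Its cost is that secondary results with nominal P below 0.05 could no longer be presented as effects.
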